1. Participants will complete the Daily Inventory of Stressful Events (DISE; see attached document) survey once per day, for 8 consecutive days. The DISE survey will be completed using online software (Qualtrics; accessed via institutional contract), which significantly minimizes participant burden. The DISE survey can be completed on any device with internet connectivity (smartphone, tablet, laptop, desktop computer, etc.).
2. This survey takes ~10-15 minutes to complete per day and consists of ~100 questions. The main types of information that will be obtained using the DISE include questions about the types of daily stressors (e.g., argument with a friend, work/school deadlines, malfunctioning computer), how the stressor made you feel

(e.g., angry, nervous), feelings of psychological distress (e.g., anxiety, irritability), and daily physical symptoms. Participants will also be asked questions about stress related to the COVID-19 pandemic. Participants are free to skip any questions that they prefer not to answer.

3. Participants are familiarized with the organization, flow, and types of questions in the DISE prior to participation.
4. A laboratory team member will send the participant both a text message and an email every day for the 8 consecutive days of the assessment, and these reminder texts/emails will contain information on how to access the DISE survey.
5. The DISE survey will be scheduled such that on Day 8 (i.e., the last day of the daily stressor assessment), the participant will return to the lab for one of the experimental visits (described below). The second experimental visit will be scheduled on Day 9 (i.e., one day after the last day of the daily stressor assessment).

Assessment of Daily Physical Activity and Sleep

1. 24-hour movement behaviors will be assessed using an accelerometer. This assessment will occur during the same sampling timeframe as the Assessment of Daily Stressor Processes described above. Participants will be asked to wear an accelerometer on the wrist of their non-dominant hand or hip for 24 hours a day except during aquatic activities, and to keep wearing it for 8 consecutive days. The accelerometer will be numbered to each participant with his/her age, gender, height, and weight information uploaded in advance. The participant will receive specific verbal and written instructions for the use of the accelerometer (See "Actigraph instructions").

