#### **4.3 Statistical Design and Power**

***Data Analytical Plan:*** Two psychosocial stressor exposure indicators will be calculated: stressor frequency (i.e., percentage of interview days during which at least one stressor occurred) and total stress (i.e., total number of stressors reported across all interview days). The emotion item ratings will be averaged to obtain daily negative affect scores, and scores will be aggregated for the 8 interview days. Negative affective reactivity will be defined as the magnitude of the change in negative affect on days when stressors occurred compared to negative affect on non-stressor days. Negative affective reactivity scores will be calculated using two-level multi-level modeling, as previously described. Muscle SNA will be quantified as burst occurrence (burst frequency) and size (burst area) and will be assessed during an overall baseline and in response to each laboratory-applied stressor. Beat-to-beat sympathetic transduction to the vasculature and to BP will be determined via spike-triggered averaging. Although daily stressor exposure and negative affective reactivity are the primary outcomes, exploratory analyses will expand our model of daily stress processes to examine the heterogeneity of the types of stressors experienced (stressor diversity) in relation to sympathetic reactivity in adults with MDD, which will provide additional insight to stress system dysfunction in depression and form the basis of subsequent proposals.

***Statistical Approach:*** To ensure robust and unbiased results, we will use defined protocols for classifying and testing subjects. For all aims, multiple experimental controls and orthogonal approaches are used, and relevant biological variables are factored into the research design and analyses. Data analysis will be blinded, when applicable, and performed by two independent investigators. Statistical significance will be accepted at  $p<0.05$ . Given our strict inclusion criteria, in order to achieve the required sample size of MDD patients, we will oversample young adults with MDD; healthy non-depressed adults will be recruited and matched on a 1:1 basis, such that an equivalent number of participants will be enrolled and tested in each group.

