Multiple linear regression will be used to assess the relation between the primary outcome variable (sympathetic reactivity; continuous response variable) and two predictors: daily stressor processes (exposure and negative affective reactivity; continuous variables) and MDD (dichotomous between-group variable). The interaction between daily stressor processes and group will also be included in the model, such that:

$$\text{sympathetic reactivity} = \beta_0 + \beta_1 * \text{MDD} + \beta_2 * \text{daily stressor process} + \beta_3 * \text{MDD} * \text{daily stressor process} + e$$

In this model,  $\beta_0$  is the intercept,  $\beta_{1/2/3}$  are the regression coefficients for each variable (group, daily stressor process, and the interaction), and  $e$  is the random error, assumed to be normally distributed, with a mean of zero and constant variance. We hypothesize  $\beta_3$  will be significant such that the effect of daily stressor exposure (Aim 1) and negative affective reactivity (Aim 2) on sympathetic stress reactivity will be stronger in adults with MDD. All models will be tested with and without person mean stressor exposure to account for potential group differences in the frequency of daily stressor exposure. Sensitivity analyses will examine the effect of depressive symptom severity (continuous variable) instead of using the dichotomous MDD variable.

Sample size calculations are based on a power analysis for the squared semi-partial correlation between the response variable and each predictor that remains after controlling for the effect of the other predictor. Our preliminary data indicate the model  $R^2=0.40$ , with the two squared semi-partial correlation coefficients as 0.30 (stressor exposure) and 0.16 (group). Since a squared semi-partial correlation coefficient as low as 0.15 can be considered clinically relevant (medium effect size), a total sample size of 55 is a conservative estimate to detect a significant partial correlation between the response variable and each predictor after controlling for the effect of the other predictor (80% power at  $\alpha=0.05$ ; t-test). For negative affective reactivity, a sample size of 48 is a conservative estimate to detect a significant interaction effect (80% power at  $\alpha=0.05$ ; t-test). To account for attrition and potential experimental failure, we will test a total of 80 participants (40/group).

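### Minor, cheap improvement: agreement of the two planned Aim 2 runs (with and without mean stressor exposure) cannot show that the Aim 2 interaction is separate from the Aim 1 interaction; one added MDD × exposure run would address this

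*SAP*

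**What the plan says.** SAP section 4.3 (Statistical Approach) gives one regression equation for both aims: group, one daily stressor process, and their product. On the product it says "The interaction between daily stressor processes and group will also be included in the model". The process is stressor exposure in Aim 1 and negative affective reactivity in Aim 2, and both hypotheses rest on the product coefficient β3.

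The only planned adjustment for exposure is one sentence: "All models will be tested with and without person mean stressor exposure to account for potential group differences". It continues with the purpose, "to account for potential group differences in the frequency of daily stressor exposure". It does not say how the covariate enters, names no product of MDD with it, and gives no rule for reading the pair of runs.

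The Data Analytical Plan in the same section defines two exposure indicators, "stressor frequency (i.e., percentage of interview days during which at least one stressor occurred) and total stress (i.e., total number of stressors reported" over the interview days. Neither is called a person mean, but the purpose clause points to stressor frequency. The Protocol (Assessment of Daily Stressor Processes) collects the diary "survey once per day, for 8 consecutive days".

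**The concern.** Aims 1 and 2 each posit a steeper slope in MDD, one for exposure and one for affective reactivity to it. Both measures come from the same diary and may be correlated. If they are, and Aim 1 is true, a reactivity × MDD coefficient can appear because reactivity stands in for exposure. A reader who sees β3 hold up with and without the exposure covariate could take this as proof that the reactivity interaction stands apart from the exposure interaction. The planned pair of runs cannot support that reading, because the term that would separate the two, MDD × exposure, is in neither run.

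**Working it through.** **1. The plan's own figure.** The SAP says: "For negative affective reactivity, a sample size of 48 is a conservative estimate to detect a significant interaction effect". It gives 80% power and α = 0.05 but no effect size. Solving the noncentral F (two-sided, 4 parameters) for 80% power at N = 48 gives f² ≈ 0.171. This value is used below for cost only.

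**2. Algebra.** Let X be exposure and Z reactivity, both standardised, with corr(X, Z) = rho. Code G = ±0.5 for group, with equal groups. Suppose

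y = b·X + delta·G·X + theta·G·Z + e.

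Within each group X = rho·Z + r, so G·X = rho·G·Z + G·r. With balanced groups, G·r is uncorrelated with 1, G, Z, G·Z and also X. A model without G·X therefore estimates

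β3 = theta + rho × delta,

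whether or not X is included. Adding G·X returns theta. The carry-over is zero if rho or delta is zero.

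**3. Size.** The SAP supplies N = 80 (40 per group). Assumed: rho, delta, b² = 0.15, residual variance 0.60, theta = 0. Rejection of β3 at nominal 5%, 20,000 simulated datasets per row:

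| rho | delta | rho × delta | no covariate | + X | + X and G·X |
|---|---|---|---|---|---|
| either 0 | either 0 | 0 | 5% | 5% | 5% |
| 0.3 | 0.39 | 0.117 | 9% | 10% | 5% |
| 0.5 | 0.39 | 0.195 | 16% | 19% | 5% |
| 0.5 | 0.5 | 0.25 | 24% | 27% | 5% |

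In the last row mean β3 is 0.251, 0.251 and 0.002, as the algebra predicts.

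For scale, b = √0.15 = 0.387. Delta 0.5 then means slopes of 0.637 in MDD and 0.137 in controls, a ratio of 4.6; delta 0.39 gives a ratio of 3.0. With the SAP's preliminary 0.30 in place of 0.15 the ratios are 2.7 and 2.1.

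The simulation is not calibrated to the SAP's R² of 0.40. Outcome variance is 0.15 + 0.25 × delta² + 0.60, which is 0.75 to 0.81, so R² is 0.20 to 0.26.

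A separate set of assumptions (slope 0.3, interaction 0.8, residual SD 1, rho 0.5) gives the same pattern: mean β3 0.403, 0.401 and 0.003 against 0.5 × 0.8 = 0.40, and rejection 31%, 38% and 5%.

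**4. What agreement shows.** Take rho = 0.5, mean β3 about 0.25, and datasets where the run without the covariate is significant. The main-effect run is also significant in 84% of them when β3 is pure carry-over (theta 0, delta 0.5) and in 86% when it is a real distinct effect (theta 0.25, delta 0). Agreement hardly distinguishes the two.

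**5. Where the main effect does help.**
- Exposure level differing by 0.8 SD between groups (delta 0, rho 0.5): β1 moves from 0.31 to 0.00 and β2 from 0.19 to 0.00. β3 is 0.00 in both runs.
- Exposure–reactivity correlation of 0 in controls and 0.5 in MDD, with a common exposure slope: β3 moves from 0.195 (17% rejection) to 0.001 (5%).

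**6. Aim 1.** If the covariate is stressor frequency, it is identical to the predictor in the Aim 1 frequency model. The columns intercept, group, predictor, product and covariate then have rank 4 of 5, so that run adds nothing. β3 is not harmed.

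**7. Limit of the added run.** If the outcome depends on usual exposure and the diary measures it with reliability rel, the added run keeps a carry-over of rho·delta·(1 − rel)/(1 − rel·rho²). At rho = delta = 0.5 and assumed rel 0.7 this is 0.25 × 0.3/0.825 = 0.091 (7% rejection); at rel 0.5 it is 0.25 × 0.5/0.875 = 0.143 (10%).

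**The case against.** **The plan makes no error.** The runs have one declared purpose, to allow for group differences in exposure frequency, and a main effect meets it. Neither document claims that the Aim 2 effect is distinct from exposure. This stands. A reader might infer that the planned Aim 2 test is invalid or has an inflated error rate. The documents do not support that: β3 from the equation as written is the overall group difference in the reactivity slope, which is what Aim 2 asks. The rejection rates above are errors only for the narrower claim of separation.

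**The covariate is not really undefined.** A reader might also infer that it is. The same sentence refers to the frequency of exposure, and stressor frequency is defined just before, so that is the likely meaning. The SAP also cites method sources that are not available here. What remains is to say so explicitly.

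**Main-effect entry is an assumption.** True. If the authors intend an MDD × exposure product, the concern falls away once they write it down.

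**The size depends on two unknowns.** Also true. With rho at most 0.3 and delta at most 0.39 the rejection rate is at most 10%, and the 24/27% figure needs a strong correlation together with a large slope difference.

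**The product term costs precision, and diary error leaves it imperfect.** Both are correct. They are reasons to make it a sensitivity analysis, not the primary model.

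**Conclusion.** The point holds as a minor, inexpensive improvement. If the covariate enters as a main effect, neither planned Aim 2 run can separate a reactivity interaction from an exposure interaction, so their agreement is not evidence of separation. The algebra is general for balanced groups with the same exposure–reactivity correlation in each. The size is not known: it runs from no excess (rho or delta zero), through 9/10% at rho 0.3 and delta 0.39, to 24/27% at rho = delta = 0.5, all on assumed values at N = 80. There is no contradiction and no wrong figure in the SAP. The planned main-effect run is worth keeping, because it corrects β1 and β2 for level differences and β3 when the exposure–reactivity correlation differs by group.

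**What to change.** Keep both planned runs and add to SAP section 4.3:

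> Person-mean stressor exposure is stressor frequency as defined in the Data Analytical Plan [or name the other indicator, if that is meant]. It enters as a main effect and is omitted from the Aim 1 model built on the same indicator. For Aim 2, one further sensitivity run includes person-mean stressor exposure and MDD × person-mean stressor exposure; β3 is reported with its CI. An Aim 2 interaction distinct from exposure will not be claimed on the unadjusted or main-effect runs alone. Any such claim will note that exposure comes from up to 8 diary days, so some carry-over may remain.

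This needs no new data. The cost is a wider CI for β3 in the added run. Against the main-effect run its SE grows by at most a factor of about 1/√(1 − rho²): 1.05 at rho 0.3, 1.15 at 0.5 and 1.40 at 0.7. In simulation the increase is up to about 5%, 12–16% and about 40%.

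Using the back-calculated f² = 0.171, reduced to 0.171 × (1 − rho²) with 6 parameters, the added run needs N = 53, 64 and 93 for 80% power at rho 0.3, 0.5 and 0.7. With all 80 complete its power is 94%, 88% and 74%; with 55 completers it is 82%, 74% and 57%. It is therefore proposed as a sensitivity analysis, with no change to the sample size.

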To test our hypotheses, we will enroll healthy adults having no history of mood disorders and adults with major depressive disorder (MDD) having a broad range of depressive symptom severity. After screening, subjects will meet with the research coordinator or an investigator for a discussion, with opportunity for questions, before applicable consent forms are obtained. Daily stress processes will be assessed using an ecological momentary assessment approach for 8 consecutive days. On the last day of the daily stress assessment, we will directly measure muscle sympathetic nerve activity, blood pressure, and heart rate during acute laboratory-based cognitive, emotional, and physiological interventions to induce a stress response. A venous blood sample will be taken for measurements of metabolic and renal health and systemic inflammation.

Aim 1: To examine the effect of daily psychosocial stressor exposure on acute sympathetic stress reactivity in MDD. Two stressor exposure indicators will be calculated: stressor frequency (i.e., percentage of interview days during which at least one stressor occurred) and total stress (i.e., total number of stressors reported across all interview days) and will be related to the magnitude of responsiveness to the acute stress interventions. We hypothesize that the slope of this relation will be steeper in adults with MDD compared to healthy non-depressed adults.

Aim 2: To determine the relation between negative affective reactivity to daily psychosocial stressor exposure and acute sympathetic stress reactivity in MDD. Negative affective reactivity will be calculated as the change in affect on days when stressors occurred compared to one's typical affect on non-stressor days and will be related to the magnitude of responsiveness to the acute stress interventions. We hypothesize that the slope of this relation will be steeper in adults with MDD compared to healthy non-depressed adults.

Detailed Description:

Conditions

Conditions: Major Depressive Disorder

Keywords:

Study Design

Study Type: Interventional

Primary Purpose: Basic Science

Study Phase: N/A

Interventional Study Model: Single Group Assignment

Number of Arms: 1

Masking: None (Open Label)

Allocation: N/A

Enrollment: 100 [Anticipated]

Arms and Interventions

| Arms | Assigned Interventions |
|---|---|

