| 
Experimental: Assessment of Daily Stress Processes
 
Subjects will report cumulative exposure, perceived severity, and emotional responsiveness to commonly occurring everyday psychosocial stressors utilizing an ecological momentary assessment approach for 8 consecutive days.
 | 
Acute Stressors
 
Sympathetic nervous system activity and blood pressure will be measured before, during, and after several acute laboratory-based cognitive (Stroop Color Word Test), emotional (International Affective Picture System), and physiological (Cold Pressor Test) stressors.
 |

Outcome Measures

Primary Outcome Measure:

1. total number of daily stressors

[Time Frame: 8 days before intervention]

2. change in negative affect in response to daily stressors

[Time Frame: 8 days before intervention]

3. change in muscle sympathetic nerve activity in response to acute stress (compared to resting baseline activity)

[Time Frame: during laboratory-based intervention (3 minutes)]

Eligibility

Minimum Age: 18 Years

Maximum Age: 30 Years

Sex: All

Gender Based:

Accepts Healthy Volunteers: Yes

Criteria:**Inclusion Criteria:**

- All participants will be 18-30 yrs.
- Healthy non-depressed men and women will have no history or evidence of psychiatric illness and will not have a family history of MDD or major psychiatric illness.
- Men and women with MDD will have symptomatic depression that meets diagnostic criteria and will be non-medicated.
- The capacity and willingness to provide written informed consent, to attend all study related visits, and to comply with the study protocol.

Exclusion Criteria:

Subjects will be excluded at the discretion of the PI/collaborating clinician or for any of the following reasons:

- psychiatric illness aside from MDD (including current or past psychotic disorders, bipolar disorder, schizophrenia or schizoaffective disorder, panic disorder, post-traumatic stress disorder, obsessive compulsive disorder)
- subthreshold depression
- current use of psychotropic medications (including major classes of antidepressants, anxiolytics, antipsychotics, mood stabilizers)
- active suicidal or homicidal ideation
- active substance dependence or eating disorders
- current use of any medications that could alter sympathetic reactivity
- diagnosed or suspected cardiovascular, renal, or metabolic disease (hypertension, heart disease, diabetes, hyperlipidemia)
- autonomic disorders
- tobacco use (including electronic cigarettes)

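### The Aim 2 regression enters negative affective reactivity without the affect level it is measured from, so it cannot separate reactivity from usual mood

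*SAP*

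**What the plan says.** Aim 2 in the Protocol's registry record is "To determine the relation between negative affective reactivity to daily psychosocial stressor exposure and acute sympathetic stress reactivity in MDD", with a steeper slope expected in MDD. Registered primary outcome 2 is "change in negative affect in response to daily stressors".

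SAP 4.3, Data Analytical Plan, defines the score as the "change in negative affect on days when stressors occurred compared to negative affect on non-stressor days". On method it says only: "Negative affective reactivity scores will be calculated using two-level multi-level modeling, as previously described". Daily negative affect is itself scored, and "scores will be aggregated for the 8 interview days".

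SAP 4.3, Statistical Approach, models sympathetic reactivity on MDD (β1), the daily stressor process (β2) and their product (β3): "The interaction between daily stressor processes and group will also be included in the model". Two further steps are planned:

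- "All models will be tested with and without person mean stressor exposure", to allow for groups meeting stressors at different rates.
- "Sensitivity analyses will examine the effect of depressive symptom severity (continuous variable) instead of using the dichotomous MDD variable".

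No model is said to contain non-stressor-day or mean negative affect.

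**The concern.** A change score is often related to the level it starts from. People whose negative affect is high on ordinary days may also react more to stressors. The Protocol recruits MDD participants across a wide span of symptom severity, so usual affect will plausibly vary a good deal within that group. The MDD term removes the average mood difference between groups but not this within-group variation.

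If usual affect is itself related to the nerve response, the planned model gives part of that relation to reactivity. A significant Aim 2 result could then mean that stronger reactions to daily stressors go with a larger sympathetic response, or that being lower in mood generally does. These are different findings, and the planned output would not tell them apart.

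**Working it through.** **The plan's own figure.** The total of 55 reproduces with f² = 0.15, two-sided α = 0.05, 80% power and one tested coefficient (noncentral F, λ = f²N). The 48 given for the Aim 2 interaction has no stated effect size; it needs f² of about 0.1725. Neither figure is in dispute. They serve below to price the fix.

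**Where the omitted level goes.** Suppose reactivity has no effect and affect level has slope γ in each group (γ0 controls, γ1 MDD). Let r0 and r1 be the within-group level-reactivity correlations, with level and reactivity scaled to SD 1. Leaving level out gives, on average:

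- β2 = γ0·r0
- β3 = γ1·r1 − γ0·r0

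So β3 is shifted when γ or r differs by group. When both are equal, the shift is in β2 alone.

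**Size with exactly known slopes.** Assume γ = 0.5 residual SD, so level explains 0.25/1.25 = 20% of outcome variance where it acts. The residual variance in a group is 1 + γ²(1 − r²). With 40 per group, SE(β3) ≈ √[(v0 + v1)/37] and the critical t on 76 df is 1.99.

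| Assumed case | Shift in β3 | SE | Approx. rejection | Simulated (4,000 runs) |
|---|---|---|---|---|
| Level in MDD only, r = 0.3 | 0.15 | √(2.2275/37) = 0.245 | 9% | 9.5% |
| Level in MDD only, r = 0.5 | 0.25 | √(2.1875/37) = 0.243 | 17% | 17.7% |
| Level in MDD only, r = 0.7 | 0.35 | √(2.1275/37) = 0.240 | 30% | 29.5% |
| Equal level effect, r = 0.2 and 0.6 | 0.20 | √(2.40/37) = 0.255 | 12% | 12.8% |
| Equal level effect, r = 0.5 in both | 0 | – | 5% | 4.6% |

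In the last row the shift is in β2: 0.25 with SE √(1.1875/37) = 0.179, about 28% (simulated 28.8%). With level and MDD × level added, the β3 rates in the rows with a shift return to 4.6-5.4%.

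**Size with scores from an 8-day diary.** Assumed: level explains 15% of outcome variance in MDD only; intercept SD 1, slope SD 0.7, day-level SD 1.0; stressor-day probability 0.4 in controls and 0.5 in MDD; 40 per group; 1,500 runs per cell. Ranges are across repeated simulations.

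| r | β3 significant, known slopes | β3 significant, two-level predicted slopes |
|---|---|---|
| 0.3 | 6-9% | 15-18% |
| 0.5 | 13-15% | 24-26% |
| 0.7 | 23-26% | 31-35% |

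- Adding mean stressor exposure leaves these rates unchanged (17%, 25%, 34% with predicted slopes).
- Adding level and MDD × level returns them to about 5%.
- If level explains 30%, the predicted-slope rates are about 32%, 49% and 66%.
- If level explains 15% in both groups alike, β3 stays near 5%, and β2 is significant in 9-59% of runs over the same r values and both kinds of score.
- With r = 0 and known slopes, β3 stays near 5%.

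**Price of the companion model.** Two extra terms cost almost no degrees of freedom: at f² = 0.15 and N = 80, power is 92.8% with three or five terms. Overlap is what costs. Taking f² = 0.15(1 − r²), power at N = 80 is 90%, 84% and 69% for r = 0.3, 0.5 and 0.7.

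**The case against.** Five points stand against reading too much into this.

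1. A reader might infer that the planned test has an inflated type I error. The documents do not support that. Aim 2 and the SAP hypothesise a steeper slope in MDD and nowhere claim it is independent of mood level. In the scenarios above where β3 shifts, the unadjusted slopes really do differ by group, so rejecting β3 = 0 is correct for the hypothesis as written. The problem is one of attribution.
2. A reader might infer that any mood effect will appear in β3. It will not: an equal level effect with an equal correlation leaves β3 near 5%.
3. The plan is not silent on severity. Using severity in place of MDD gives partial protection. With severity assumed to track level closely, its interaction was significant in roughly 10-15% of runs where level explained 15%, against 25-35% for the main model at r = 0.5-0.7. That is a reduction, not a solution, because no model puts affect level and its product with MDD beside reactivity.
4. The first stage is given only by citation. Centring, covariates and type of score are unknown, so the higher predicted-slope figures are conditional. Unshrunken person-level differences gave 7%, 8% and 13% at r = 0.3, 0.5 and 0.7.
5. Adjusting a change for its reference level is debatable when both may express one trait, and the adjusted estimate is less precise. This supports placing the adjusted model beside the planned one, not in its place.

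**Conclusion.** The omission is plain in SAP 4.3, and neither planned safeguard closes it. As specified, Aim 2 can show that the reactivity slope differs by group but cannot say whether this reflects reactivity or usual affect. The documents do not fix how large this is. The 6-26% (known slopes) and 15-35% (predicted slopes) for β3 rest on an assumed level effect confined to MDD, an assumed 15% of variance and assumed correlations of 0.3-0.7. Under an equal effect and equal correlation the ambiguity moves to β2, and with no correlation and known slopes it disappears. This is a cheap improvement to what Aim 2 can conclude, not a flaw that invalidates the planned test.

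**What to change.** In SAP 4.3, Statistical Approach, for Aim 2:

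- Pre-specify one companion model that adds each person's centred non-stressor-day negative affect and its product with MDD. State how that level is obtained from the diary.
- Report β2 and β3 with confidence intervals from both models, and the correlation between reactivity score and affect level in each group.
- Describe a result as specific to reactivity, rather than to usual mood, only with reference to the adjusted estimate and its interval. Set no pass/fail rule on how much of β3 must survive.

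The cost is a few lines of text and one extra model on data already collected. The downside is precision. In simulation with a true reactivity effect explaining 30% of variance in MDD and r = 0.3-0.5, power for β3 fell from 80% to 67-75% with known slopes, and from about 51-57% to 27-35% with predicted slopes. An adjusted interval that includes zero would therefore be weak evidence against a reactivity effect, and the planned model should stay primary.
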